5. HANDLING OF MISSING VALUES

Should missing data occur, the data will be analysed as they are recorded in the eCRFs, and no imputation of missing data will be performed.

All data analysis in this study will be performed on the Full Analysis Set containing all patients who fulfil the eligibility criteria, and thus missing data is not used as criteria for excluding the patients from the data analysis. However, due to the nature of the study, there will likely be missing data for data elements, ie, data that are not documented in the patient's medical record.

For both categorical and continuous variables, the amount of missing data will be reported. For categorical variables, the missing values will be analysed in the descriptive summary tables as a category. The missing values in the continuous variables will be ignored when calculating the summary statistics of mean, median, standard deviation and quantiles. If some of the variables of interest show to have a large amount or proportion of missing data, the summary statistics of the variable should be interpreted accordingly.

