6.3. Analysis for the Exploratory Objectives

For the exploratory analyses, time to response (TTR), time to progression (TTP)/ progression free survival (PFS) will be studied and results will be presented as shown in [Table Shell 54](#). The stratified tables will be presented as in Table Shells [55-61](#).

TTR is defined as the length of time (in days) from the initiation of Palbociclib treatment until the first reported disease response (complete or partial).³⁴ Censoring rules presented in [Section 3.1](#) will be applied.

TTP is defined as the length of time (in days) from the initiation of Palbociclib treatment until the first reported disease progression.³⁴ Patients will be censored at the end of Palbociclib treatment, death, time of withdrawal, or end of the 24-month follow-up, whichever occurs first, at the respective time point. Specifically, death is not included in TTP but is considered as censoring event.

PFS is defined as the length of time (in days) from the initiation of Palbociclib treatment until the first reported disease progression or death due to any cause, whichever occurs first.³⁴ The disease progression will be considered at the first follow-up visit after the Palbociclib treatment initiation when the overall tumor response recorded is progressive disease. Patients with no disease progression documented will be censored at the last available medical record entry or end of the follow-up period. Patients who are lost to follow-up will be censored at their last visit.

Survival analyses will be used to estimate time to event endpoints TTR, TTP and PFS. The results of the survival analysis will be presented as the Kaplan-Meier survival curves and their 95% confidence intervals (CIs) that will be calculated using the log-log transformation of the survival probabilities.³⁶ Together with the Kaplan-Meier plots, the number of patients at risk at time intervals (eg, 90 days or as seen appropriate for the study) will be reported. [Figure Shells 1 and 2](#) show how time to response (TTR) and progression free survival (PFS) will be visualized as Kaplan-Meier plots including the number of patients at different time intervals. Kaplan-Meier plots can be presented by other categories (see [Section 3.2](#)), if enough data are available. Moreover, the results of the survival analysis will be reported as a descriptive summary table including the number of patients at risk, the number of patients

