Treatment completed	Palbociclib treatment characteristics (secondary endpoint)	At Palbociclib treatment discontinuation	CRF sheet: Palbociclib treatment discontinuation form	
 Yes (reason of discontinuation is "Completion of planned course of treatment"); no (other reason or censored)
Duration of Palbociclib treatment	Palbociclib treatment characteristics (secondary endpoint)	At Palbociclib treatment discontinuation	CRF sheet: Palbociclib treatment discontinuation form	
 Time (in days) from first to last day in Palbociclib treatment
Another treatment after discontinuing treatment with Palbociclib	Palbociclib treatment characteristics (secondary endpoint)	At Palbociclib treatment discontinuation	CRF sheet: Palbociclib treatment discontinuation form	
 Yes No
Reason for end of follow-up	Clinical outcomes (primary endpoint)	At last visit	CRF sheet: End of Observation/ End of Study Follow Up	
End of follow-up will be categorised as:
 
 Death Patient withdrawal Lost to follow-up End of 24-months follow-up period
Concomitant medications	Clinical characteristics (secondary endpoint)	At Palbociclib treatment initiation, At follow-up visits	CRF sheet: Concomitant Medications Form	Open field. 10 most common will be listed.
Supportive therapies	Supportive therapies (secondary endpoint)	At the initiation of Palbociclib treatment	CRF sheet: Supportive Therapies Form	The type of the supportive therapies received by the patients since the BC diagnosis. Open field. 10 most common will be listed.
Comorbidities	Clinical characteristics (secondary endpoint)	At the initiation of Palbociclib treatment	CRF sheet: Comorbidities form	Open field. 10 most common comorbidities will be listed
Proportion of progression free patients	Clinical outcomes (primary endpoint)	At the follow-up visits	CRF sheet: Tumor Assessment Form and End of follow-up	The proportion of the patients who are alive and for whom no progression of the disease has been reported.
Progression free survival (PFS)	Clinical outcomes (exploratory endpoint)	At the follow-up visits	CRF sheet: Tumor Assessment Form and End of follow-up	The time from the Palbociclib treatment initiation until the progression of the disease or death to any cause, whichever occurs first.

PFIZER CONFIDENTIAL

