Table Shell 14 - Descriptive summary table of Palbociclib treatment characteristics.

Missing	XX (xx%)
None, reason specified	XX (xx%)
Yes, specified treatment	XX (xx%)
Tamoxifen/NOLVADEX	XX (xx%)
Toremifene / FARESTON	XX (xx%)
Raloxifene / EVISTA	XX (xx%)
Anastrozole / ARIMIDEX	XX (xx%)
Letrozole / FEMARA	XX (xx%)
Exemestane / AROMASIN	XX (xx%)
Fulvestrant / FASLODEX	XX (xx%)
Goserlin Acetate / Zoalox	XX (xx%)
Leuprorelin / Lupron	XX (xx%)
Triptorelin / Decapeptyl	XX (xx%)
Degarelix / Firmagon	XX (xx%)
Interruption in the cycle	
Yes	XX (xx%)
No	XX (xx%)
Missing	XX (xx%)
Reasons for the cycle interruption	
Lab abnormalities	XX (xx%)
Decline in ECOG performance score	XX (xx%)
Presence of comorbidities	XX (xx%)
Patient request	XX (xx%)
Concomitant medications	XX (xx%)
Other	XX (xx%)
Missing	XX (xx%)
Modification in the dose and/or the schedule	
Dose modified	XX (xx%)
Schedule modified	XX (xx%)
Both modified	XX (xx%)
Neither modified	XX (xx%)
Missing	XX (xx%)
Reasons for the dose and/or schedule modifications	
To avoid toxicity	
Due to line of therapy received	XX (xx%)
ECOG performance score	XX (xx%)
Age	XX (xx%)
Presence of comorbidities	XX (xx%)
Patient request	XX (xx%)
Disease progression	XX (xx%)
Poor adherence	XX (xx%)
Developed resistance to endocrine treatment	XX (xx%)
Metastases status	XX (xx%)

PFIZER CONFIDENTIAL

Table Shell 14 - Descriptive summary table of Palbociclib treatment characteristics.

Stage at the breast cancer diagnosis	XX (xx%)
Concomitant medications	XX (xx%)
Other	XX (xx%)
Missing	XX (xx%)
Delays in the cycle	
Yes	XX (xx%)
No	XX (xx%)
Missing	XX (xx%)
Reasons for the delays in the cycle	
Lab abnormalities	XX (xx%)
Adverse events	XX (xx%)
Decline in ECOG performance score	XX (xx%)
Presence of comorbidities	XX (xx%)
Patient request	XX (xx%)
Concomitant medications	XX (xx%)
Other	XX (xx%)
Missing	XX (xx%)
Reasons for discontinuation	
Toxicities of side effects	XX (xx%)
Patient decision	XX (xx%)
Patient physical status	XX (xx%)
Disease progression	XX (xx%)
Completion of planner course of treatment	XX (xx%)
Developed resistance to endocrine treatment	XX (xx%)
Poor adherence	XX (xx%)
Death	XX (xx%)
Treatment related toxicity	XX (xx%)
Non-treatment related toxicity	XX (xx%)
Patient request	XX (xx%)
Lost to follow-up	XX (xx%)
Other	XX (xx%)
Treatment completed	
Yes	XX (xx%)
No, reason specified	XX (xx%)
Missing	XX (xx%)
Duration of Palbociclib treatment [days]	
N	XX (xx%)
Mean (SD)	xx.x (xx.x)
Q1, median, Q3	xx.x, xx.x, xx.x

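### Duration of palbociclib treatment is a right-censored time that the SAP summarises as an ordinary continuous variable, with no rule for patients still on treatment at month 24

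*SAP*

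**What the plan says.** SAP Section 4.2 lists duration and discontinuation among the palbociclib treatment characteristics that form a secondary endpoint. Annex 1 Table 3 defines duration as "Time (in days) from first to last day in Palbociclib treatment", collected at discontinuation, with source "CRF sheet: Palbociclib treatment discontinuation form".

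Reaching month 24 is recorded elsewhere. "End of 24-months follow-up period" is a reason for end of follow-up on the end-of-study form and is not among the listed reasons for discontinuation. Death and loss to follow-up are on that list.

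Section 5 states that "no imputation of missing data will be performed" and that "The missing values in the continuous variables will be ignored when calculating the summary statistics of mean, median, standard deviation and quantiles". Table Shell 14 (Annex 2 numbering) gives duration as N, mean (SD), quartiles, range and Missing, and Shells 15-21 repeat this by subgroup. None has a censored or ongoing row.

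Section 6.3 sets the scope of the time-to-event methods: "Survival analyses will be used to estimate time to event endpoints TTR, TTP and PFS". Table Shell 54 reports the number censored for those three endpoints.

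The neighbouring variable, treatment completed, does foresee censored patients; its second category is "no (other reason or censored").

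**The concern.** Follow-up stops at 24 months, so a patient still taking palbociclib then has a duration known only to exceed 24 months. A definition that needs a last treatment day, a source completed at discontinuation, and a rule that leaves missing values out together remove exactly the longest-treated patients. The resulting error can only be downward.

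The subgroup tables would suffer unequally: the subgroup with the most patients still on treatment loses the most information, so differences by combination (Shell 15) or line (Shell 16) would be compressed.

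Two related rows share the problem. Coding censored patients as not having completed treatment pools them with patients who stopped, although Shell 14 expects a reason for every such patient. The discontinuation-reasons block has no ongoing or missing row and no stated denominator.

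**Working it through.** The plan gives no expected duration or persistence, so there is no figure of its own to reproduce. The check asks what median the literal rules would return.

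**Inputs.** Cut-off 24 months (SAP Section 3.1) and N = 200 (Protocol Section 8.1). As an assumption, time on treatment S(t) follows progression-free survival as quoted in Protocol Section 6.1: medians of 24.8 months (phase III letrozole trial), 20.2 months (phase II letrozole trial) and 9.5 months (fulvestrant trial), and US real-world first-line rates of 75.5% at 12 and 51.6% at 18 months.

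**Formula.** The completed-only median t* solves 1 − S(t*) = [1 − S(24)]/2.

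**Exponential with median m.** S(t) = 2^(−t/m), so t* = −m × log2{1 − [1 − S(24)]/2}.
- m = 24.8: S(24) = 0.511; t* = −24.8 × log2(0.756) = 10.0 months.
- m = 9.5: S(24) = 0.174; t* = −9.5 × log2(0.587) = 7.3 months.

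**Weibull through the real-world rates.** Shape k = ln[ln(1/0.516)/ln(1/0.755)]/ln(18/12) = 2.11; scale = 18/[ln(1/0.516)]^(1/k) = 21.9 months. The median is 21.9 × (ln 2)^(1/k) = 18.4 months, S(24) = 0.297 and t* = 14.7 months.

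| Assumption | Ongoing at month 24 | Assumed true median | Completed-only median | Shortfall |
|---|---|---|---|---|
| Exponential, 24.8 | 51% | 24.8 | 10.0 | 60% |
| Exponential, 20.2 | 44% | 20.2 | 9.6 | 52% |
| Weibull, real-world rates | 30% | 18.4 | 14.7 | 20% |
| Exponential, 9.5 | 17% | 9.5 | 7.3 | 23% |
| Exponential, 6 | 6% | 6.0 | 5.5 | 9% |
| Exponential, 4 | 2% | 4.0 | 3.9 | 2% |

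A simulation at the 20.2-month median (200 patients, 4,000 runs) agrees: the mean completed-only median is 9.6 months (95% range 7.6 to 11.8), from about 112 of the 200 patients.

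**Subgroup contrast, as illustration.** Assumed true medians of 24.8 and 9.5 months differ 2.6-fold (24.8/9.5). The completed-only medians differ 1.4-fold (10.0/7.3).

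**Alternative: ongoing patients entered at 24 months as if complete.** The medians become 24.0, 20.2, 18.4 and 9.5 for the first four rows, so the median is nearly right. The mean is not: for the exponential with median 24.8 it is 17.5 months, against 24.8/ln 2 = 35.8. The third quartile is exactly 24 months in each of the first three rows, where 25% or more are ongoing; for that same exponential the true value is 2 × 24.8 = 49.6 months.

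**The case against.** A reader might infer that the SAP orders ongoing patients to be discarded. No section says so; it follows only from combining the definition, its source and Section 5. There are signs the other way. Section 3.1 censors continuing treatment at 24 months, Section 5 describes expected missing data as items absent from the medical record, and the treatment-completed variable, from the same form, allows for censored patients. An analyst could reasonably enter 24 months, and the median bias then almost vanishes. This stands as a limit on the claim. It does not rescue the plan, because the mean and often the third quartile remain artefacts of the window. Section 3.1 also makes end of palbociclib treatment itself a censoring point, which cannot serve for a variable whose event is the end of treatment.

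A reader might also infer that the median will be far too short. The documents do not support that as a general statement. They contain no time-on-treatment data, the 60% figure needs the longest quoted median and an exponential shape, and the real-world rates under a Weibull give 20%.

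Nor can it be said that patients lost to follow-up have no last day. Loss to follow-up is a listed discontinuation reason, so they may have a form entry. Their time would then be counted as complete when it is censored, which also pulls the estimate down.

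Finally, the analysis is descriptive, the stratified tables are exploratory, N and Missing would be visible, and the Kaplan-Meier examples in Section 6 are not exhaustive. All true, but a reader of Shell 14 could not tell an undocumented duration from an ongoing one, and Section 6.3 does not extend survival methods to duration.

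**Conclusion.** The concern holds in this form: a named secondary endpoint that is right-censored has a summary method with no provision for censoring. Followed literally, it biases the median downward, by about 20% to 60% if time on treatment resembles the progression-free survival figures in the protocol, and by 2% to 9% if median persistence is only 4 to 6 months. On the alternative reading the median is nearly right, but the mean is truncated and the third quartile is fixed at 24 months whenever at least a quarter of patients are ongoing. The direction under the literal reading is certain; the size rests on an assumption the documents do not make. The ambiguity matters in itself: with a true exponential median of 24.8 months, two analysts following this SAP could report 10.0 and 24.0 months from the same data. The change should be made before analysis.

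**What to change.** Analyse time on palbociclib by Kaplan-Meier. The event is permanent discontinuation for any reason, including death. Patients still on treatment, withdrawn while on drug, or lost are censored at the last known treatment date or month 24, whichever is earlier. State this rule for the variable itself, since it departs from the general rule in Section 3.1.

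In Table Shells 14-21:
- report the median, quartiles and percentage on treatment at 6, 12, 18 and 24 months, with 95% confidence intervals;
- add an ongoing/censored row separate from Missing;
- split the No category of treatment completed into discontinued and ongoing/censored;
- use discontinued patients as the denominator for discontinuation reasons.

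The cost is SAP wording, a few shell rows and code of the kind already planned for progression-free survival. Treatment status and date at last contact are needed; the treatment cycle form named in Annex 1 Table 3 is a possible source, to be confirmed against the CRF. The median may be not reached in some subgroups, which the percentages on treatment would cover.

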6.2. Analysis for the Secondary Objectives

The objective response rate (ORR) will be described as shown in [Table Shell 2](#) and stratified in [Table Shells 3-9](#). The objective response will be defined as a state when either complete or partial response or stable disease has been reported as the overall tumor response in the last follow-up visit. ORR will be calculated as the ratio of the number of patients who are responsive to Palbociclib treatment (ie, have partial or complete response or stable disease for Palbociclib treatment recorded) over the number of patients who initiated Palbociclib treatment.³⁴ Censoring will be considered as described in [Section 3.1](#).

The demographic characteristics of the study population at breast cancer diagnosis for those receiving Palbociclib as first or second line therapy for metastatic/locally advanced BC will be described as shown in [Table Shells 10 and 11](#). Clinical characteristics of the study population at the initiation of Palbociclib treatment (baseline) those receiving Palbociclib as first or second line therapy will be described as shown in [Table Shells 12 and 13](#).

The dosing and dose changes, interruptions, delays and discontinuations associated with Palbociclib use in clinical practice will be described as shown in [Table Shell 14](#). The stratified tables will be presented as in [Table Shells 15 – 21](#).

The ten most common supportive therapies received by patients while receiving palbociclib combination treatment will be listed as shown in [Table Shell 22](#). The stratified tables will be presented as in [Table Shells 23 - 29](#).

The most common adjuvant therapies including systemic therapies, radiotherapy and surgeries will be described for early or locally advanced BC (stages 0-IIIa) patients as shown in [Table Shell 30](#). The stratified tables will be presented as in [Table Shells 31– 37](#).

The most common adjuvant therapies received by the advanced/metastatic BC patients (stages IIIB-IV) will be described both before and immediately after the first Palbociclib treatment as shown in [Table Shells 38 and 62](#), respectively. The stratified tables will be presented as in [Table Shells 39-45 and 63-69](#).

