CT24-WI-GL03-RF02 2.0 Non-Interventional Statistical Analysis Plan For Primary Data Collection Study 01-Jun-2020

Page 43 of 172

0901776099673e30A5481150 Palbociclib Read On: 28-Mar-2023 09:56 (GMT)

Variable	Role	Time point(s)	Data source(s)	Operational definition
Time to progression (TTP)	Clinical outcomes (exploratory endpoint)	At the follow-up visits	CRF sheet: Tumor Assessment Form and End of follow-up	The time from the first breast cancer diagnosis to the first reported progression of the disease or death from the disease, whichever occurs first.
Objective response rate (ORR)	Clinical outcomes (secondary endpoint)	At the follow-up visits	CRF sheet: Tumor Assessment Form	The proportion of the patients who have been reported to be responsive (partial or complete response or stable disease) for the treatment.
Time to first response	Clinical outcomes (exploratory endpoint)	At the follow-up visits	CRF sheet: Tumor Assessment Form	The time from the first breast cancer diagnosis to the first reported response (partial or complete response) for the treatment.
Proportion of overall survival	Clinical outcomes (primary endpoint)	At 1 and 2 years after the treatment initiation	CRF sheet: Tumor Assessment Form and End of follow-up	The proportion of alive patients over all patients who initiated the treatment.
Item	Quality of life (secondary endpoint)	At follow-up visits	CRF sheet: Patient reported outcomes (PROs)	There are 28 questions (items) in EORTC-QLQ-30 questionnaire that are classified as follows: 1: Not at all 2: A little 3: Quite a bit 4: Very much
Item	Quality of life (secondary endpoint)	At follow-up visits	CRF sheet: Patient reported outcomes (PROs)	There are 4 questions (items) in EORTC-QLQ-30 questionnaire that are classified as follows: 1 (Very Poor) - 7 (Excellent)

BC=breast cancer; CBC=complete blood count; ECOG=Eastern Cooperative Oncology Group; EORTC QLQ-C30=European Organization for the Research and Treatment of Cancer Quality of Life Questionnaire Core 30; MBC=metastatic breast cancer.

10. ANNEX 2

Table Shell 1 – Summary of patients enrollment per country and site.

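### Three rows of SAP Annex 1 Table 3 (TTP, time to first response, supportive therapies) contradict SAP 6.2 and 6.3 on the time window, and for TTP also on how death is handled

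*SAP*

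**What the plan says.** SAP 6.3 is explicit on TTP: "TTP is defined as the length of time (in days) from the initiation of Palbociclib treatment until the first reported disease progression". On deaths it adds: "Specifically, death is not included in TTP but is considered as censoring event". The same section measures time to response from palbociclib initiation to the first complete or partial response.

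Annex 1 Table 3, in its operational definition column, gives TTP as "The time from the first breast cancer diagnosis to the first reported progression of the disease or death from the disease, whichever occurs first" and time to first response as "The time from the first breast cancer diagnosis to the first reported response (partial or complete response) for the treatment". Both rows carry the role of exploratory clinical outcome. The PFS row of the same table starts at palbociclib initiation.

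For supportive therapies, SAP 6.2 says: "The ten most common supportive therapies received by patients while receiving palbociclib combination treatment will be listed". Annex 1 Table 3 describes the variable as "The type of the supportive therapies received by the patients since the BC diagnosis" and gives palbociclib initiation as its time point.

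SAP 4.4 names Table 1 and Table 3 (Annex 1) as the place for detailed definitions of the data entry schedule and variables. It then says that the definitions of clinical outcomes are in Sections 6.1 to 6.3.

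**The concern.** A programmer who derives variables from the annex will not produce the analyses described in Section 6. TTP and time to response would then mix disease history with time on treatment, although the exploratory objective (Protocol 7.3, SAP 2.2.3) is about outcomes associated with palbociclib combination treatment. TTP would also count some deaths that 6.3 censors. The supportive-therapy table, titled for the palbociclib period, could be filled from a variable that reaches back to diagnosis. Because the row's time point is initiation, it could even be filled with pre-treatment care only. Nothing in the output would flag any of this.

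**Working it through.** The point concerns definitions, and the plan has no figure of its own to reproduce. The first step sets the passages side by side.

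| Item | Annex 1 Table 3 | Body of the SAP |
|---|---|---|
| TTP, start | First breast cancer diagnosis | Palbociclib initiation (6.3) |
| TTP, event | Progression or death from the disease | Progression only; death censored (6.3) |
| Time to response, start | First breast cancer diagnosis | Palbociclib initiation (6.3) |
| Supportive therapies, window | Since diagnosis; time point at initiation | During palbociclib treatment (6.2; also 2.2.2, 4.2, Table Shell 22 and Protocol 7.2) |

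**Effect of the starting point.** Let L be a patient's interval from first diagnosis to palbociclib initiation, and T the time from initiation to progression or response. Under 6.3 the value is T; under the annex it is L + T. For a patient who progresses, Table Shell 54 would show a PFS of T beside a TTP of L + T for the same progression date. L already has its own Annex 1 row (time since initial diagnosis), so there is no sign that TTP was meant to contain it.

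Patients enter at palbociclib initiation (SAP 3.1), and the TTP and response rows draw on follow-up assessments. With a diagnosis origin the interval L is therefore event-free by design, which is left truncation, and no delayed-entry method is planned. L is near zero for de novo disease treated at once and longer for recurrent disease. The planned table by metastatic status (Table Shell 59) would show a difference even if time on treatment were identical.

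**Illustrative size.** The documents give no value for L and no share of deaths without recorded progression, so both are assumptions here.

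- Anchor: the 18-month PFS of 51.6% that Protocol 6.1 cites from a US first-line chart review. With an exponential curve the hazard is -ln(0.516)/18 = 0.6616/18 = 0.03676 per month.
- Death counted as an event, all deaths assumed to be from cancer: median = ln 2/0.03676 = 18.9 months.
- Death censored as in 6.3, with a share s of PFS events being deaths without recorded progression: median = 18.86/(1 - s). For s = 5%, 10% and 20% this is 19.9, 21.0 and 23.6 months. The death rule alone therefore lowers the median by about 1, 2 and 5 months.
- Diagnosis as origin, with the same L for everyone: 18.9 + 12 = 30.9, 18.9 + 36 = 54.9 and 18.9 + 60 = 78.9 months for L of 12, 36 and 60 months.
- If L exceeds 24 months for everyone, the annex TTP curve stays at 100% through month 24 on its own time axis.

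Time to response shifts by the same L.

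**What is not affected.** SAP 6.1 measures the progression-free proportions from the beginning of palbociclib treatment. The Annex 1 rows for proportion progression-free, PFS and overall survival do not use diagnosis as origin.

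**The case against.** The strongest reply is SAP 4.4. It sends clinical outcome definitions to 6.1-6.3, and SAP 3.1 sends outcome-specific censoring to the same sections. Annex 1 itself labels TTP and time to response as clinical outcomes. A programmer who follows that pointer will use 6.3 and get the intended result. This stands as a reason to think the error less likely for these two variables. It does not remove the conflict, because the same section names Table 3 for detailed variable definitions.

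For supportive therapies, the objective, endpoint, method and table title all give the palbociclib period, and only one annex row differs. A note to the data entry schedule says supportive care is collected in the metastatic setting, so the annex row may describe a wider collection window rather than the analysis. That is plausible, but the pointer in 4.4 does not reach this variable and no other rule says which text governs.

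A reader might infer more than the documents support:

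- That a relapse before palbociclib could count as the first progression. The TTP row's time point is the follow-up visits and its sources are the tumor assessment and end-of-follow-up forms, so earlier relapse lies outside it.
- That every patient gains a spurious event-free period. De novo patients treated at once gain almost none.
- That the inflation can be set against medians of 9.5 to 24.8 months. Those are PFS medians from the randomised trials in Protocol 6.1; they are not TTP or time-to-response medians.

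**Conclusion.** The contradictions are in the current SAP text, and the annex rows would give wrong results if programmed as written. The affected outcomes are exploratory (TTP, time to response) and secondary (supportive therapies), so this should be corrected but does not threaten the primary results. The distortion in TTP and time to response equals each patient's diagnosis-to-palbociclib interval, which the documents do not quantify. The medians of about 31, 55 and 79 months rest on assumed common lags of 12, 36 and 60 months, an exponential curve and one cited PFS figure; they show direction and scale only. The effect of counting cancer death, about 1 to 5 months on the median, rests on an assumed 5% to 20% share of such deaths. For supportive therapies the consequence is a table covering the wrong period; its size cannot be computed from the documents.

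**What to change.** Amend three rows of Annex 1 Table 3:

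- TTP: start at the date of palbociclib initiation; event is documented progression only; death is censored, as in 6.3.
- Time to first response: start at the date of palbociclib initiation, as in 6.3.
- Supportive therapies: those received while on palbociclib combination treatment, as in 6.2, including any recorded at the initiation visit that continue on treatment. Restricting the row to follow-up visits would risk dropping those. Change the time point to match.

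The cost is three table cells and one time-point entry, with no new data collection. The SAP needs revision anyway: it was written from protocol version 2.0 and still plans 350-410 patients and 12 months of recruitment (SAP 2.1), against about 200 patients and 18 months in Protocol 8.1.
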